## 3. Quality Performance Indicators

Multiple practice guidelines have been published for the management of AP (14–19). The recommendations in these guidelines are usually based on a systematic review of the relevant literature and the evidence on which is based on the available evidence, which is usually graded. Quality performance indicators will be drawn from these evidence-based recommendations for each of the nominated management domains that are relevant to the management of patients within the first 72 hours from admission to hospital. Any differences in the recommendations between the source guidelines will be resolved by discussion amongst the Scientific Advisory Group and consensus established for the QPIs.

The QPIs were developed for the following management domains: (Appendix D: Table 1 with guidelines)

**Table 1.** Quality Performance Indicators

	Domain	QPI	Ref*	Metrics
1	Diagnosis	All patients diagnosed within 12 hours of admission	IAP	RAC criteria for diagnosis: enzymes 3xUL, typical pain ± CT scan
2	Aetiology	All patients had tests for aetiology determined within 24 hours of admission	IAP	U/S for gallstones ETOH history with intake (units per week, timing of binge to pain) If both negative then lipids, IgG4, drugs
3	Severity (predicted)	All patients had prediction of severity on admission	IAP	N / Y, if yes method (drop-down of all options and other) Further drop-down bar will the give options for severity (mild, moderate, and severe)

4	Severity (actual)	All patients had actual severity determined at 48 hours	-	N / Y, if yes method (drop-down RAC, DBC and other) Further drop-down bar will the give options for severity (mild, moderate, and severe)
5	CT scan	Initial CT assessment performed after 72-96 hours if poor response to initial management or clinical deterioration, unless there is diagnostic uncertainty. Not required for severity prediction.	IAP	N / Y, if yes indication (drop-down with other)
6	Transfer	All patients with predicted or actual severe AP in the first 72 hours are discussed with specialist pancreas service.	Nice	N / Y Indication for transfer (drop-down)
7	Analgesia	All patients given narcotic analgesia within one hour of admission	-	Step-up or step-down approach? IV analgesia given on admission N / Y NSAIDS given to mild AP Analgesics prescribed

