All hospital leads will also be required to complete a hospital-survey which assess hospital-related variables (*Appendix C*).

Data collection will occur at two timepoints. The first time point will be within or at 48 hours of admission to hospital and secondly at 30-days follow-up following admission to the emergency department .

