**Appendix A (i) - Revised Atlanta Classification of AP severity**

Severity	Definition
Mild acute pancreatitis	Absence of organ failure Absence of local complications
Moderately severe acute pancreatitis	1. Local complications AND/OR 2. Transient organ failure (<48 hours)
Severe acute pancreatitis	1. Persistent organ failure (>48 hours)

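### QPI 4 sets actual severity at 48 hours, apparently from admission, a time at which Appendix A (i) cannot yet class as severe any organ failure that began at or after admission

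*Protocol*

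**What the plan says.** Protocol section 3, Table 1 row 4 (actual severity) states the indicator as "All patients had actual severity determined at 48 hours". Its metric is "N / Y, if yes method (drop-down RAC, DBC and other"), followed by "Further drop-down bar will the give options for severity (mild, moderate, and severe"). RAC is the revised Atlanta classification; the other listed methods are not defined.

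Appendix A (i) is the only severity classification in the document. Severe disease is "Persistent organ failure (>48 hours"). The organ-failure limb of moderately severe disease is "Transient organ failure (<48 hours"). Mild disease requires that there be no organ failure and no local complication.

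On timing, section 3 takes the indicators from recommendations "relevant to the management of patients within the first 72 hours from admission to hospital". Section 5.3 says: "The first time point will be within or at 48 hours of admission to hospital". Section 5.6 describes a 72-hour early follow-up instead.

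Actual severity appears again in Table 1 row 6: "All patients with predicted or actual severe AP in the first 72 hours are discussed with specialist pancreas service". Two secondary aims in section 2 stratify outcome analyses by severity without saying which grade is meant.

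**The concern.** The two rules appear to use different clocks. Row 4 seems to count from admission, whereas Appendix A (i) counts from the onset of organ failure. A grade fixed 48 hours after admission would then be made before the severe criterion can be met by any failure that started in hospital.

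QPI 4 is part of the overall compliance outcome and of the comparison between hospitals by domain. On a strict reading, a team that waits until persistence is established misses the time, while a team that grades on time records a class that may have to change. If the 48-hour grade were carried into the severity strata, or into the actual-severe limb of QPI 6, the severe class would be largely empty.

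**Working it through.** The plan gives no figure to reproduce here. The check sets the two time rules against each other.

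**Inputs.** Assessment time T = 48 h (row 4). Origin: admission, inferred from sections 2, 3 and 5.3. Severe: duration above 48 h. Transient: duration below 48 h (both Appendix A (i)).

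**Formula.** Organ failure that starts t hours after admission and is still present at T has lasted T − t hours. Severe requires T − t > 48, that is t < T − 48.

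| Onset t (h from admission) | Duration at hour 48 | Result on the organ-failure criterion |
|---|---|---|
| −1 | 49 h | severe |
| 0 | 48 h | neither above nor below 48 h, so no class |
| 12 | 36 h | not severe |
| 30 | 18 h | not severe |
| after 48 | not yet begun | mild, if there is no local complication |

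**Latest onset that can be graded severe.**
- T = 48 h: t < 0, so before admission only.
- T = 72 h: t < 24 h.
- T = 96 h: t < 48 h.

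**Share of eventually severe patients who can be graded severe.** Let q be the share with onset before admission, and assume that the other onsets are spread evenly over the first H hours. The share at T is q + (1 − q) × min(1, (T − 48)/H). The documents give neither q nor H, so both are assumptions.

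- At T = 48 the second term is zero and the share equals q: 0%, 5%, 10% or 20% for those values of q. This does not depend on H, or on how onsets after admission are distributed.
- At T = 72:
  - q = 0: 100% for H = 24, 24/48 = 50% for H = 48, and 24/72 = 33% for H = 72.
  - q = 0.2: 100%, 0.2 + 0.8 × 0.5 = 60%, and 0.2 + 0.8 × 0.333 = 47%.

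So at hour 72 the share runs from about 33% to 100%, depending on the assumed onset pattern.

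**QPI 6.** Setting T = 72 shows that its actual-severe limb can reach only failure with onset before hour 24. The protocol does not say this.

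**The case against.** Several points limit the concern.

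- **The clock is inferred.** Row 4 says only 48 hours, whereas rows 1, 2, 7, 9 and 12 name admission. Section 5.3 sets a data-collection time, not an indicator clock. Admission remains the likelier reading, since sections 2 and 3 use it and nothing in the protocol counts row 4 from organ-failure onset. It should still be labelled an inference.
- **QPI 4 does not score accuracy.** A grade made at 48 hours passes whatever its value, and methods other than the revised Atlanta classification are allowed. Patients who never develop organ failure face no conflict. Both points stand, so the direct effect on the primary outcome is confined to a minority.
- **The use of the grade is not stated.** A reader might infer that the severity strata will be emptied. The protocol does not say that the 48-hour grade defines them. Section 5.5 lists a predicted-severity field but no actual-severity field. Its 30-day block holds material for a later grade: renal failure beyond 48 hours, durations of organ support, and local complications. That material is incomplete, and no rule says to use it, so the harm to the strata is conditional.
- **Misclassification is not uniform.** A reader might also infer that every truly severe patient lands in the moderately severe class. That does not follow. Onset before admission can be graded severe, onset exactly at admission has no class on this criterion, and onset after hour 48 without local complications would be graded mild.
- **QPI 6 is narrowed, not contradictory.** Severe disease can be established within 72 hours when onset is before hour 24, and the row also covers predicted severe disease. The matching field in section 5.5 asks only about predicted severe disease, so the listed data would not score the actual limb in any case.

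**Conclusion.** The conflict between row 4 and Appendix A (i) holds, on the inference that row 4 counts from admission and for grades made by the revised Atlanta classification. At hour 48, no patient whose organ failure began at or after admission can be graded severe, and a duration of exactly 48 hours falls between the two classes. The share that escapes this is the share with onset before admission, which the documents do not give.

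Sites can still comply with QPI 4. Two consequences follow from the text as it stands: a strict reading counts a team that waits to establish persistence as late, and a 48-hour grade under-classifies patients whose failure is ongoing and persists, or starts later and persists. A largely empty severe class would follow only if that grade were used for the strata or for the actual-severe limb of QPI 6. The protocol neither states nor rules out that use.

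**What to change.** - Reconcile row 4 with Appendix A (i): state the clock for row 4, and assign a duration of exactly 48 hours to a class.
- For scoring QPI 4, accept a grade documented by 48 hours as provisional for all patients, including those without organ failure. Do not count a later update in a patient with ongoing organ failure as non-compliance.
- For every analysis that uses actual severity, including the strata and the actual-severe limb of QPI 6, use a grade derived from local complications and from organ-failure onset and end over the 30-day follow-up, not the 48-hour entry.
- State that the actual-severe limb of QPI 6 within 72 hours covers only organ failure with onset before hour 24.

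The cost is wording plus onset and end dates and times for each organ-failure item. Section 5.5 now records only whether renal failure exceeded 48 hours and how many days organ support lasted, from which the grade can be rebuilt only in part. The change concerns scoring and analysis and leaves patient care as it is.

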## 2. Aims

### Primary Aim:

To measure adherence with quality performance indicators (QPIs) for the management of AP during the first 72 hours after admission in AoNZ.

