## 5.5. Required data

Demographic details	
Age	Year of birth
Sex	Male/ Female/ Other
Ethnicity	European/ Pasifika/ Maori/ Asian/ Middle-Eastern/ Latin American/ African (MELAA)/ other ethnicity
Postcode	
Weight	kg
Height	cm
Smoking history	Current smoker /previous smoker /never smoker e-cigarette /cigarette
Admission details	
Date of first review by doctor/prescriber	Date (dd/mm/yyyy)  *From ED admission note
Time of first review by doctor/prescriber – as per admission note	24 hour clock time
Pancreatic enzymes at admission	Lipase/ Amylase/ Pancreatic amylase (tick one or more and give admission level and indicate what 3x upper limit is
Lipase/ amylase/ pancreatic amylase level	U/L
Epigastric pain confirmed on admission note	Yes/Non-epigastric abdominal pain/ No abdominal pain
Confirmation of AP diagnosis with imaging as per radiological report	MRI/ CT/ Abdominal USS
Charlson Comorbidity Index ( Appendix E )	Score out of 37
Aetiology	
Significant ETOH history investigated in first 72 hours	Yes - from medical history, Yes - ETOH blood test, No

Hypertriglyceridemia investigated in first 72 hours	Yes/No
Acute pancreatitis severity	
Predicted severity on admission as documented in clinical notes (72 hours)	Mild/ moderately severe/ severe
Method used to predict severity	Modified Glasgow/ Ransons'/ BISAP/ APACHE II/ SIRS/ CRP (>150)/ Other (please specify)/ Clinical judgement (no prediction tool)/ No prediction made.
Imaging	
CT assessment performed in the first 72 hours of presentation	Yes/ No
Indication for CT prior to 72 hours	Diagnostic uncertainty/ confirmation of severity based on clinical predictors of severe AP/ Failure to respond to conservative treatment or in the setting of clinical deterioration/ other (please specify)
Imaging of the gallbladder during admission	USS/ CT (gallstones seen on CT)/ MRI/ EUS/ prior imaging confirming gallstones/ previous cholecystectomy/ no imaging
Antibiotics	
Antibiotics administered in first 72 hours of presentation	Yes/ No
Indication for antibiotics	Cholangitis concomitant extrapancreatic infection/ prophylactic/ other – please state
Analgesia	
Simple analgesia (paracetamol/ NSAIDs) prescribed	Paracetamol/ NSAIDs/ Not charted
Simple analgesia frequency	regular/ PRN
Date simple analgesia first administered	Date (dd/mm/yyyy)

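### QPI 5 describes a CT after 72-96 hours, but the dedicated CT items stop at 72 hours, so an omitted indicated CT can never be identified as non-compliance

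*Protocol*

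**What the plan says.** Table 1 (Section 3), row 5, defines the indicator: "Initial CT assessment performed after 72-96 hours if poor response to initial management or clinical deterioration, unless there is diagnostic uncertainty". It adds that CT is "Not required for severity prediction". The Metrics column asks for yes or no and, if yes, an indication from a drop-down. It asks for no time.

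The Primary Aim (Section 2) measures adherence "during the first 72 hours after admission in AoNZ". The introduction to Section 3 likewise confines the indicators to management in the first 72 hours from admission.

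The Imaging block of Section 5.5 has two dedicated CT items. One is "CT assessment performed in the first 72 hours of presentation", answered yes or no. The other is "Indication for CT prior to 72 hours". Its options include diagnostic uncertainty, "confirmation of severity based on clinical predictors of severe AP" and "Failure to respond to conservative treatment or in the setting of clinical deterioration".

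**The concern.** The action in row 5 falls after the window that the dedicated CT items observe, and after the window of the aim. Two things follow.

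- **Omission is invisible.** If a patient responds poorly and never has a CT, the form shows 'No'. It shows the same for a patient who never needed one.
- **Early CT for deterioration is unclassified.** Row 5 as worded excuses only diagnostic uncertainty. The form records deterioration as a separate reason for early CT, and the protocol does not say whether that answer is compliant.

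QPI 5 is one of twelve indicators behind the primary outcome (Section 4.1). It also feeds the between-hospital comparison by domain (Section 4.2), and the funnel plots and the models of clinical outcome by compliance (Section 8). If 'No' passes, a hospital that under-images gains. If early CT for deterioration fails, patients enter the non-compliant group because they deteriorated. The outcome comparison would then partly reflect the illness and not the care, and the stratification by severity in the Secondary Aims may not fully remove this.

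**Working it through.** The protocol states no compliance rate or target for QPI 5, so there is no figure to reproduce. The check sets each possible course against what the form records.

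**Step 1: what each answer covers.** A CT after 72 hours for poor response or deterioration is taken to satisfy row 5.

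- 'No', no indication, no CT: row 5 met.
- 'No', no indication, later CT: unclear from row 5.
- 'No', indication present, CT after 72 hours: row 5 met.
- 'No', indication present, CT never done: row 5 not met as worded.
- 'Yes', diagnostic uncertainty: row 5 met through the stated exception.
- 'Yes', confirmation of severity: row 5 not met as worded.
- 'Yes', failure to respond or deterioration: row 5 not met as worded, but no classification is given.

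Four courses share the answer 'No'. One of them is a failure, and it cannot be separated from the other three.

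**Step 2: can another item separate them?**

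- The gallbladder imaging item in Section 5.5 covers the whole admission and offers CT as an option. It has no date and no link to deterioration.
- The 30-day items record local complications and organ failure. They give no CT date or indication.
- No item records poor response or deterioration in a patient without an early CT.

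So the distinction cannot be recovered from the data as specified.

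**Step 3: possible size of the omission effect.** Suppose every 'No' were scored compliant. Let p be the share of patients who meet the condition and o the share of those whose CT is omitted. Then

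overstatement of the QPI 5 rate = p × o.

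The only related figure in the protocol is the 20% with moderate or severe disease (Section 1), used here as an assumed stand-in for p. The values of o are assumptions.

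- p = 20%, o = 10%: 0.20 × 0.10 = 2 points
- p = 20%, o = 25%: 0.20 × 0.25 = 5 points
- p = 20%, o = 50%: 0.20 × 0.50 = 10 points
- Outer range, p from 10% to 30% and o from 10% to 100%: 0.10 × 0.10 = 1 point, up to 0.30 × 1.00 = 30 points

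**Step 4: effect on the overall rate.** The protocol does not state how the twelve indicators combine. If the overall rate were a simple mean of the twelve, 2 to 10 points on QPI 5 would move it by 2/12 = 0.2 to 10/12 = 0.8 points. If it required all twelve to be met, the shift could not exceed the 2 to 10 points, because only patients who meet the other eleven would change status.

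**Step 5: the deterioration category.** Counting it one way or the other moves the QPI 5 rate by exactly its share of the patients scored. The form records that share, so it need not be assumed.

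**The case against.** The strongest reply is that the form matches row 5's own Metrics column, which asks only yes or no and the indication. Read with the 72-hour aim, the measurable content is whether an early CT was done and why. On that reading the data are adequate and only the wording of row 5 is too wide. This is fair, and it is the basis of the second remedy below. It does not remove the mismatch, because row 5 as written still describes a later CT that the study will not see.

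Three stronger readings are tempting, and the documents do not support them.

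- **An omitted CT always scores as compliant.** A reader might infer this, but the protocol has no rule for scoring a 'No'. It could count as compliant, not applicable or not assessable, and an analysis plan may settle it. What the protocol does show is that omission cannot be identified. No scoring rule can repair that, because the data are not collected.
- **The form contradicts Table 1 on early CT for deterioration.** This would require every listed reason to be an acceptable one. The same list holds confirmation of severity, the antibiotic list holds prophylaxis despite QPI 10, and the nil-by-mouth list holds an unknown reason despite QPI 11. The lists sort reasons and do not endorse them. The category is captured and can be scored either way, so it is an unclassified category and not a contradiction.
- **A CT must be done by 96 hours.** Row 5 gives an earliest time and no latest one. A scan at 110 hours would satisfy it, and a 96-hour cut-off on the form would be arbitrary.

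The 20% is also a weak stand-in. Moderately severe disease can be defined by local complications (Appendix A (i)), and necrosis is defined by contrast CT criteria (Appendix B). Some of those patients have therefore already been imaged.

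**Conclusion.** The point holds in a limited form. Row 5 and the dedicated CT items cover different periods, and an indicated CT that was never done cannot be found in the dataset. The data can therefore support a statement about early CT and its reasons, but not one about adherence to row 5 as written. Separately, early CT for deterioration needs a stated classification, because counting it as non-compliant would load deteriorating patients into the non-compliant group of the outcome comparison.

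The size cannot be derived from the documents. The illustrative 2 to 10 points on QPI 5 rests on three assumptions: every 'No' is scored compliant, 20% meet the condition, and 10-50% of those have the CT omitted. The effect on the overall rate also depends on a combination rule that the protocol does not give, and under a simple mean of twelve it is below one point. The change is worth making because the gap cannot be filled at analysis and is cheap to close beforehand. Which CT timing is clinically right is outside this review.

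**What to change.** Reconcile row 5 with Section 5.5, without choosing a CT timing, in one of two ways.

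- **(a) Collect what row 5 needs.** Add the date and time of the first CT during the admission, with no 96-hour cut-off, and a yes/no item for poor response or deterioration with its time. Both can be taken from the notes at the 30-day chart review already planned in Section 5.6. Cost: two or three extra fields per patient, and an indicator that then reaches past the 72-hour aim, which should be stated.
- **(b) Report what is observed.** Restrict the scored and reported indicator to CT in the first 72 hours by indication, and state that omission of a later CT is not assessed. Cost: a wording change, and QPI 5 then claims less.

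In both cases the Scientific Advisory Group should classify each listed indication as compliant, non-compliant or not assessable before data lock. The report should show the QPI 5 rate with the deterioration category counted each way. This needs no new data beyond the chosen option.

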### 5.4. Patient eligibility

#### *Inclusion Criteria*

- All patients  $\geq 16$  years old who present with AP, as defined by the revised Atlanta criteria (*Appendix B*)
- Presenting to a public hospital that manages acute patients in AoNZ.

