Type of opioid prescribed (if any)	Codeine/ Morphine/ Fentanyl/ Tramadol/ Oxycodone/ Other (please specify)/ no opioids prescribed
Date opioid analgesia first administered	Date (dd/mm/yyyy)
Time opioid medication is administered to patient	24 hour clock
Route	PO/ IV
(If regular) daily dose	mg
(If PRN) total dose in first 72 hours	mg

(If yes) Date opioids first administered	Date (dd/mm/yyyy)
(If yes) Time opioid medication first administered as per drug chart?	24 hour clock
Further analgesic modalities	PCA/ ketamine/ local nerve blocks/ other (please specify)
Transfer to different hospital	
Patients with predicted severe disease discussed with specialised pancreas service ( Appendix B ) in first 72 hours from admission	Yes/ No/ not applicable
Patient transferred to a different hospital in the first 72 hours?	Yes/No
(If yes) Date of transfer	Yes/No
(If yes) Location transferred to	List of hospitals
(If yes) Reason for transfer to different hospital?	Severe disease/ requires ERCP/ requires interventional management of local complication/ other (free text)
ERCP	
Cholangitis in first 72 hours ( Appendix F )	Yes/ No
Cholestasis in first 72 hours (radiological + deranged LFTs)	Yes/ No
ERCP performed in the first 72 hours	Yes/ No
Fluid management*	
Baseline variables	
Bag 1	
Date of administration	Date (dd/mm/yyyy)
Time of administration	Time (24-hour)
Volume administered	Volume (ml)
How long does fluid run for?	Time (hours)
Type of fluid	0.9% Normal saline/ Hartmann's/ plasmalyte/ colloid/ 0.45 saline + dextrose/ 0.18 saline + dextrose/ other (please specify)
Further administration of intravenous fluid (IVF) in the first 3 days of admission? ( Appendix B )	Yes/no
Bag 2	
Date of administration	Date (dd/mm/yyyy)
Time of administration	Time (24-hour)

Volume administered	Volume (ml)
Time fluid is administered	Time (hours)
Type of fluid	0.9% Normal saline/ Hartmann's/ plasmalyte/ colloid/ other (please specify)
Further administration of intravenous fluid (IVF) in the first 2 days of admission?	Yes/no
Documented fluid review after 12 hours ( $\pm$ 4 hours)	Yes/no
Documented fluid review after 24 hours ( $\pm$ 4 hours)	Yes/no
Documented fluid review after 48 hours ( $\pm$ 4 hours)	Yes/no
Documented fluid review after 72 hours ( $\pm$ 4 hours)	Yes/no
Early Nutritional support	
On admission patient kept nil by mouth (NBM)	Yes/no

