**Appendix B - Definitions**

Local complication	Definition
Acute pancreatitis (AP)	
The diagnosis of acute pancreatitis requires two of the following three features:
 
 
● Abdominal pain consistent with acute pancreatitis (acute onset of a persistent, severe, epigastric pain often radiating to the back)
 
● Serum lipase activity (or amylase activity) at least three times greater than the upper limit of normal
 
● Characteristic findings of acute pancreatitis on contrast-enhanced computed tomography (CECT) and less commonly magnetic resonance imaging (MRI) or transabdominal ultrasonography (24).
 

Chronic pancreatitis (CP)	
Identification of the following signs via high quality imaging modalities (computed tomography, magnetic resonance imaging):
 
 
● Increased density of the parenchyma
 
● Atrophy of the gland
 
● Calcification
 
● Pseudocysts and irregularities of the main pancreatic duct and its side branches.
 
 
Diagnosis should be based on imaging performed in symptomatic patients presenting with indicators suggestive of pancreatic disease (25).

Specialised pancreas service	Performs elective pancreatic resections
Gallstone (biliary) AP	Confirmation of gallstones using radiological imaging (including abdominal or endoscopic ultrasonography, CT and magnetic resonance cholangiopancreatography)(14,16)
Alcohol induced AP	
History of alcohol consumption (>10g) prior to the diagnosis of acute pancreatitis.
 
10g alcohol is approximately:
 
 
● 300ml beer
 
● 100ml wine
 
● 30ml spirits
 
 
(14,16)

Hypertriglyceridaemia induced AP	
 
● Biliary and alcohol-induced pancreatitis ruled out
 
● Serum triglyceride >1,000 mg/dl ((14).
 

Necrotising AP	
Inflammation associated with pancreatic parenchymal necrosis and/or peripancreatic necrosis, CECT criteria:
 
 
● Lack of pancreatic parenchymal enhancement by intravenous contrast agent and/or
 
● Presence of findings of peripancreatic necrosis (see below—ANC and WON)(24)
 

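### QPI 7 counts all patients in its denominator, including eligible patients without abdominal pain, so its compliance rate is slightly understated

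*Protocol*

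**What the plan says.** Table 1 in section 3 of the Protocol defines the analgesia indicator as "All patients given narcotic analgesia within one hour of admission". Neither the indicator nor its metrics column mentions pain as a condition, and the reference column names no source guideline for this row.

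Section 5.4 includes patients "who present with AP, as defined by the revised Atlanta criteria" and points to Appendix B. There, "The diagnosis of acute pancreatitis requires two of the following three features": typical abdominal pain, lipase or amylase at least three times the upper limit, and characteristic imaging.

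Under admission details in section 5.5, the item on epigastric pain takes the answers "Yes/Non-epigastric abdominal pain/ No abdominal pain". The analgesia items record the type, route, dose and timing of opioid and allow for none being prescribed. They have no not-applicable answer and ask for no reason.

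Section 4.1 makes overall compliance with the indicators the primary outcome. Section 4.2 adds variation between hospitals in each domain, and section 8 plots domain compliance by hospital in funnel plots.

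**The concern.** The indicator's population is wider than the group in which early opioid analgesia can be judged. A patient admitted with enzymes above the threshold and characteristic imaging but no abdominal pain is eligible and foreseen by the form, yet can meet row 7 only by receiving an opioid. If none is given, the literal wording records a failure, although this is not the late or absent pain relief that the indicator is there to detect.

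Other rows avoid this. QPIs 5, 6, 9, 11 and 12 each carry a condition, an exception or a restriction to a subgroup, such as predicted severe disease or cholangitis. Row 7 has none.

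What is at stake is the QPI 7 domain rate, its funnel plot, any overall measure that includes it, and the comparison of outcomes between compliant and non-compliant patients in sections 2 and 8. In each, some pain-free patients would be classed with patients whose pain was not treated in time.

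**Working it through.** The Protocol states no expected compliance rate, sample size or pain-free share, so there is no figure of its own to reproduce. The check has two parts.

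**Reading the text**

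1. Eligibility follows Appendix B: two of three features (section 5.4).
2. Enzymes plus imaging makes two, so pain is not required.
3. The form has an answer for patients without abdominal pain (section 5.5), so they are expected in the data.
4. Row 7 applies to all patients, without exception.
5. Hence a pain-free eligible patient given no opioid is in the denominator and not in the numerator.

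**Size, as an illustration**

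Let p be the share of patients without abdominal pain and c the share of patients with pain who receive an opioid within the hour. Both are assumptions. Assume also that no pain-free patient receives an opioid within the hour. Then:

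- highest attainable rate = 1 − p
- reported rate = c × (1 − p)
- understatement = c × p

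With c = 60%:

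| Assumed p | Highest attainable rate | Reported rate | Understatement |
|---|---|---|---|
| 2% | 98% | 0.60 × 0.98 = 58.8% | 1.2 points |
| 5% | 95% | 0.60 × 0.95 = 57.0% | 3.0 points |
| 10% | 90% | 0.60 × 0.90 = 54.0% | 6.0 points |

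If some pain-free patients do receive an opioid within the hour, the understatement is smaller.

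**Effect on the primary outcome**

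Section 4.1 does not say how the twelve indicators combine. If they were averaged with equal weight (an assumption), an understatement of 1.2 to 6.0 points in QPI 7 becomes 1.2/12 = 0.1 to 6.0/12 = 0.5 points overall. If a patient must meet every indicator, the effect cannot be derived from the document.

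**After the change**

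With pain-free patients out of the denominator, the reported rate equals c and the highest attainable rate is 100%.

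**The case against.** The strongest reply is that the Protocol gives no scoring algorithm. How to treat patients to whom an indicator does not apply is commonly left to a statistical analysis plan, which is not at hand. The pain field is already collected, so the exclusion could be made at analysis with nothing lost. The metric for QPI 1 treats typical pain as the usual presentation, so few patients may be affected. The primary analysis is also descriptive, with no threshold to miss.

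Most of this stands, and it keeps the point small. It does not remove it: the Protocol does not leave the denominator open but states it as all patients, in conflict with its own eligibility definition. It would still be too strong to say that such patients fail by a fixed rule. Non-compliance is the literal reading of row 7, not the output of a stated algorithm.

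A reader might go further on two counts that the document does not support.

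- *Opioid given before arrival.* One field asks for "Time opioid medication first administered as per drug chart", so a reader might infer that earlier doses are missed and the patient is scored as a failure. The Protocol does not say what the drug chart contains, and a second field, "Time opioid medication is administered to patient", names no source. The time recorded under admission details is "Time of first review by doctor/prescriber", not arrival, so arrival is not even the relevant boundary. The Protocol is silent here, and no loss of compliance can be shown or sized.
- *Spurious variation between hospitals.* A reader might infer that the share of affected patients differs by hospital and so distorts the funnel plot. Nothing in the Protocol gives that share for any hospital or shows that it varies. The supported claim is a general understatement of the rate.

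**Conclusion.** The mismatch is real and rests on the text alone: row 7 includes everyone, Appendix B admits patients without pain, and the form expects them. Read as written, the indicator understates adherence to early analgesia among patients with pain.

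The effect is probably small and cannot be sized from the document. The illustrated loss of 1.2 to 6.0 points in the QPI 7 rate depends on an assumed pain-free share of 2% to 10%, an assumed adherence of 60% among those with pain, and no timely opioid in pain-free patients. The point is minor, and it concerns scoring only, not who should receive an opioid.

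**What to change.** Reconcile row 7 of Table 1 with Appendix B for scoring. State that patients coded as having no abdominal pain in the admission details are not applicable for QPI 7 and leave its denominator, in the domain rate, in the funnel plot and wherever QPI 7 enters an overall compliance measure. Patients with non-epigastric abdominal pain stay in. Report the number taken out, so that readers can see how much the rule matters.

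This takes one sentence and no new form item, because the field is already collected. The downside is a slightly smaller denominator for this domain.
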